### 9.3.1 Heterogeneity of Treatment Effects (HTE)

HTE for the primary outcomes will be assessed in six key subgroups of participants: high vs. low patient function by FAQ, high vs. low patient function by ADL, high vs low NPI-Q Severity, high vs. low MCSI at baseline, spouse caregiver vs. other caregiver, and white non-Latino vs. nonwhite or Latino (defined by PLWD for NPI-Q Severity and by caregiver for MCSI outcome). Determination of cutpoints for HTE subgroups is presented in Appendix A. These subgroup analyses are aimed at determining whether there is differential effectiveness of the interventions among patients with more and less severe disease, perhaps elucidating a preventive (if effect is greater among those with less severe disease) versus therapeutic (if effect is greater among those with more severe disease) effect. Similarly, the high vs. low distress subgroup comparison will determine whether the intervention is more effective among those with more distress at baseline (a therapeutic benefit) versus less distress (a preventive benefit). Evidence of HTE will be based on tests of interaction within the longitudinal model structure described above. Because six tests of interaction will be conducted for each outcome, we will use the Hochberg procedure to control for multiplicity using an overall type I error of 2.5% (2-sided) for each outcome; subgroup treatment differences will be reported using 99% confidence intervals.

Exploratory analyses to assess HTE for the primary outcomes will also be conducted in demographic subgroups (age, race and ethnicity) as well as the effects of the COVID-19 pandemic and not adjusted for multiplicity.

### 9.4 Analysis of Secondary Outcomes

The analysis of the continuous secondary outcomes – NPI-Q Distress, caregiver depression (PHQ-8), Caregiver self-efficacy— will be analyzed like the primary outcomes. The Hochberg procedure will be used to control for the testing of each secondary outcome using an overall type I error of 5% (2-sided); treatment differences will be reported using 95% confidence intervals.

### 9.5 Analysis of Tertiary Outcomes

The approach to the analysis of these outcomes is briefly presented; however, the actual analytic methods used will in most cases depend on the distribution of the data. A more complete analytic plan will be finalized at the time of data lock for these outcomes and the SAP will be amended accordingly. Before any analyses are conducted, data will be summarized by means, medians, ranges and box plots.

#### Continuous Outcome Scales

- Montreal Cognitive Assessment (MoCA) measured at 18 months, range 0-12
- Functional status measured at 18 months by Functional Activities Questionnaire (FAQ) , range 0-30, and activities of daily living (Katz ADL), range 0-6.
- Dementia Burden Scale-Caregiver (DBS-CG) measured at 3, 6, 12 and 18 months is a composite of the NPI-Q Distress, MCSI, and PHQ-9 scales with items transformed linearly to be on a 0-100 possible range and then averaged with higher scores indicating higher caregiver burden.
- Quality of Life in Alzheimer's Disease (QOL-AD) measured at 18 months, range 4-52.
- Caregiver's Satisfaction with Dementia Care measured at 3, 12 and 18 months, range 11-55.
- Positive Aspects of Caregiving (PAC) measured at 6 months, range 0-44.

These data will be analyzed like the primary outcomes using longitudinal models.

### Binary Outcomes

- Clinical Benefit (measured at 3, 6, 12 and 18 months) is a **binary measure** of patient symptoms using the NPI-Q severity scale (the only patient outcome anticipated to benefit from the program) and caregiver symptoms using the DBS-CG scale. Benefit on the NPI-Q severity scale is defined as having a score of  $\leq 6$  (the lowest tertile of symptoms) or improving by at least 3 points (the MCID). DBS-CG benefit is defined as having a score of  $\leq 18.8$  (the lowest tertile of symptoms) or improving by at least 5 points (the MCID). Clinical benefit is defined as having benefit on either or both component scales.

The specific endpoint for analysis remains under consideration; candidates include attainment of clinical benefit at or before a specified assessment, (discrete) time to first observed benefit, and the full set of measured clinical benefit data. Depending on the choice of endpoint, discrete time survival models, logistic regression, and GEE and mixed models for longitudinal repeated measures will be considered.

- Goal attainment scaling (measured at 6-12 and 15-18 months), defined as whether a person's individual goals are achieved as a result of the study intervention, will be measured using a 5-point goal. GAS describes the person's expected level of goal achievement over a specified timeframe, ranging from much worse than expected (scored as -2) to much better than expected (scored as +2). Scales are dynamically set according to a person's needs, while measurement of attainment is standardized. GAS is only determined for the two intervention arms: HSDC and CBDC.
  - Primary GAS outcome is the proportion who attained first identified goal at either 6 or 18 months.
  - An exploratory GAS outcome will be a repeated measures analysis of the proportion who hit target at 6 and 18 months.

GEE and mixed models for longitudinal repeated measures data will be considered.

### Count Outcome

- Caregiver Rating of Dementia Care Quality (measured at 12 months), a 10-item, yes/no instrument that contains content from ACOVE/PCPI/AAN quality measures. The outcome is a count of the number of yesses.

These data will be analyzed by Poisson, Negative Binomial, hurdle models or rank based methods depending on the distribution of the counts.

**Time spent at home** is calculated as 540 minus (1) the number of days in a health care facility, including hospital, nursing home, acute rehabilitation, and inpatient hospice, and (2) the number of days not alive. The analytic approach will depend on the distribution of the outcome. As an initial approach to the analysis, we will consider a negative binomial model assuming a potential follow-up time of 540 days. Alternatively, it may be necessary to instead analyze the complement of number of days spent at home (days dead plus days spent in a health care facility – hospital, nursing home, acute rehabilitation, and inpatient hospice) and/or use a zero-inflated model.

**Mortality** will be analyzed by the Cox regression model adjusted for site for time to event data; mortality rates will be summarized by Kaplan-Meier estimates.

**CMS data for participants** include the number of days spent in:

- Acute Care Hospital
- Inpatient Rehabilitation Facility
- Skilled Nursing Facility
- Long-term Care Facility (including time to placement)
- Hospice care

These data will be summarized by counts, means, medians and ranges. Because of the possibility of many zero counts, Poisson, Negative binomial and hurdle models will be considered. Also, because of censoring we will also consider analyzing the data similarly to time spent at home. Time to placement in a long-term care facility will be analyzed using survival methods.

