4.3.3 Early Withdrawal of Participants

Because this trial is based on the principle of “intent-to-treat”, all participants will be analyzed in the group to which the participant was randomly assigned, regardless of whether they complete the intervention or not. This preserves the effect of randomization. Because the intervention will be integrated into the work flow of the practice and community-based care, we expect relatively few withdrawals from the interventions. We will have four levels of study withdrawal:

- Withdrawal from study interventions but willing to provide study outcomes by questionnaire/interview and allow analysis of medical records and CMS claims data. Subsequent Information on health care utilization outcomes will be obtained from CMS claims data and medical records.
- Withdrawal from study interventions and willing to provide study outcomes by questionnaire/interview but unwilling to allow analysis of medical records and CMS claims data.
- Withdrawal from study interventions and unwilling to provide study outcomes by questionnaire/interview but willing to allow analysis of medical records and CMS claims data. Subsequent Information on health care utilization outcomes will be obtained from CMS claims data and medical records.
- Withdrawal from study interventions and unwilling to provide study outcomes by questionnaire/interview or allow analysis of medical records and CMS claims data. If the participant elects full withdrawal from the study, this will be recorded on the Participant Final Disposition Form and no further information will be obtained about the participant.

For participants who are lost to follow-up but who have not withdrawn from the study, we will be able to obtain information from the electronic health record or from the utilization or claims data on secondary and tertiary outcomes.

Each of the interventions will be administered until the final 18-month assessment is completed unless any of the following occur:

- Patient or caregiver withdraw and there is not a willing replacement caregiver (see 4.3.3)
- Patient Death
- Moves out of the catchment area and unable to continue to receive the intervention

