Goal attainment scaling, developed through PCORI funding to the Principal Investigator, asks patients and caregivers to select their most important goal and assesses progress towards meeting it. These goals were identified in focus groups of caregivers and patients and additional goals were identified when integrating goal-setting into clinical care in the PCORI Methodology study. An inventory of 53 dementia goals captures virtually all goals that have been articulated.¹⁷ For this study, we will use a shorter inventory designed to help caregivers consider categories of goals that may be important to them. *Goal attainment*, defined as whether a person's individual goals are achieved as a result of the study intervention, will be measured using a 5-point goal attainment scale (GAS). Using the SMART goal framework, GAS describes the person's expected level of goal achievement over a specified timeframe, ranging from much worse than expected (scored as -2) to much better than expected (scored as +2). Scales are dynamically set according to a person's needs, while measurement of attainment is standardized. The mean 6-month GAS score in a previous study of similar patients was 52.4 (SD 11.7) on a 0-100 scale with a T-score of 50 indicating that on average the expected level of goal attainment was achieved. Measurement of goal attainment will be performed with caregivers by clinicians involved in the intervention (Dementia Care Specialists and Care Consultants), who are unblinded, and can be performed over the telephone.

Conceptually, time spent at home is a composite measure of control of dementia symptoms (e.g., problem behaviors), the ability of caregivers to cope with the disease, and the success of the health system in providing

A PRAGMATIC TRIAL OF THE EFFECTIVENESS AND COST-EFFECTIVENESS OF DEMENTIA CARE/COMPARATIVE EFFECTIVENESS OF HEALTH SYSTEM-BASED VERSUS COMMUNITY-BASED DEMENTIA CARE

services that avoid days spent in other settings. Time spent at home has previously been operationalized⁴³ as within the last 6 months of life but we will modify it to include each person's total follow-up time spent after randomization that is spent at home. Total follow-up time will be determined from time of randomization to time of death, withdrawal (if CMS utilization data are allowed by the participant to be used), or to the end of the study for those who are administratively censored. Hence, the time spent at home is:

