"Number of days since randomization (540) minus (1) number of inpatient days spent at an acute care hospital, inpatient rehabilitation facility, skill nursing facility, long-term care facility, or inpatient hospice unit), and (2) number of days not alive".

Caregiver Satisfaction will be collected using a 11-item questionnaire modified from the UCLA ADC, which will be collected at 3, 12, and 18 months.

Quality of Life in Alzheimer's Disease (QOL-AD)¹⁸ is a 13-item (range 4-52) instrument that can be administered to persons with dementia and caregivers. It has demonstrated sensitivity to psychosocial intervention¹⁹ correlates with health-utility measures, is widely translated and used internationally and can be used by people with MMSE scores as low as three²⁰.

Positive Aspects of Caregiving (PAC) is measured with 11 items focusing on favorable aspects of the caregiving experience,²¹ with range 0-44 (most positive) and Cronbach's alpha 0.92.²² The items ask about their mental or affective state related to their caregiving experience. For example, providing help to care recipients has 'made me feel more useful', 'made me feel strong and confident', 'given more meaning to my life', 'enabled me to develop a more positive attitude toward life', and 'enabled me to learn new skills'.

Two additional tertiary outcomes will be examined that use measures described above.

Dementia Burden Scale-Caregiver (DBS-CG)²³ is a composite of the NPI-Q Distress, MCSI, and PHQ-8 scales with items transformed linearly to be on a 0-100 possible range and then averaged with higher scores indicating higher caregiver burden. The minimal clinically important difference (MCID) for the DBS-CG is 5 points.

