Goal attainment scaling (GAS) asks patients and caregivers to select their most important goal and assesses their progress towards meeting it as a result of one of the study's intervention. *Goal attainment scaling*, defined as whether a person's individual goals are achieved as a result of the study intervention, will be measured using a 5-point goal attainment scale. GAS describes the person's expected level of goal achievement over a specified timeframe, ranging from much worse than expected (scored as -2) to much better than expected (scored as +2). Scales are dynamically set according to a person's needs, while measurement of attainment is standardized. Measurement of goal attainment will be performed with caregivers by clinicians involved in the intervention (Dementia Care Specialists and Care Consultants), who are unblinded, and can be performed over the telephone.

4. Mortality (measured over 18 months)

Mortality as measured by interviews at 3, 6, 12 and 18 months. Data will be verified using the Center for Medicare and Medicaid Services at 18 months. For participants who did not complete the 18-month interview, vital status will be investigated using the electronic health records (EHR).

5. Time Spent at Home

Time spent at home is calculated as 540 minus (1) the number of days in a health care facility, including hospital, nursing home, acute rehabilitation, and inpatient hospice, and (2) the number of days not alive.

6. Caregiver Rating of Dementia Care Quality (measured at 12 months)

The outcome is a count of the number of yesses. Caregiver Rating of Dementia Care Quality is a composite instrument of 10 items (with yes or no responses) from the Assessing Care of Vulnerable Elders (ACOVE), Physician Consortium for Performance Improvement (PCPI) and the American Academy of Neurology (AAN) quality measures. The outcome is a count of the number of yesses (range 0-10, higher counts indicate greater caregiver rating of dementia care quality).

7. Caregiver Satisfaction with Dementia Care (measured at 3, 12 and 18 months)

Caregiver's satisfaction with the dementia care program is measured using a 11-item questionnaire, modified from the University of California Los Angeles' Alzheimer's and Dementia Care program, and ranges from 11 to 55 (higher scores indicate greater caregiver satisfaction with the dementia care program).

8. Dementia Burden Scale - Caregiver (measured at 3, 6, 12 and 18 months after baseline)

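### Time spent at home is counted from a fixed 540 days with no rule for days after a participant withdraws claims and record access, although the protocol also defines follow-up person by person

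*SAP*

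**What the plan says.** Protocol 6.1.3 introduces the outcome as "each person's total follow-up time spent after randomization that is spent at home". It continues: "Total follow-up time will be determined from time of randomization to time of death, withdrawal", or administrative end of study. A bracket attaches the withdrawal end point to participants who let their CMS data be used. The formula that follows is "Number of days since randomization (540) minus (1) number of inpatient days spent at an acute care hospital" and other facility days, and then minus days not alive. Here the person's own follow-up has become the constant 540.

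Protocol 8.2.3 and SAP 5.5 carry only the constant: "Time spent at home is calculated as 540 minus (1) the number of days in a health care facility". SAP 9.5 repeats that the outcome "is calculated as 540 minus (1) the number of days in a health care facility" and adds, as an initial approach, that "we will consider a negative binomial model assuming a potential follow-up time of 540 days". Its alternative is to analyse the "complement of number of days spent at home (days dead plus days spent in a health care facility").

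Protocol 4.3.3 sets four levels of withdrawal. At two of them the participant refuses further use of claims and medical records. One of the two keeps the interviews; the other, full withdrawal, is "unwilling to provide study outcomes by questionnaire/interview or allow analysis of medical records and CMS claims data", and nothing more is collected.

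**The concern.** The formula subtracts only two kinds of day: days known to be in a facility and days known to be after death. A day that nobody can observe is neither, so it remains in the total and is scored as a day at home, the best possible value. The complement has the mirror fault, because the same day adds nothing to the away count.

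The protocol's person-specific wording would avoid this, but neither the protocol's formula nor the SAP uses it. Missing follow-up could therefore raise an arm's mean time at home. If more people close their records in one arm than in another, part of that rise would appear as a treatment difference.

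**Working it through.** **1. The plan's own figure.** 18 months x 30 days = 540, so the constant reproduces. With calendar months, 18 x 30.4375 = 547.9. The documents give no power or target difference for this outcome.

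**2. One participant.** Let access end on day C, and let a share r of days be truly away (in a facility or dead), spread evenly.
- Literal score: 540 - r x C.
- Score with full observation: 540 x (1 - r).
- Overstatement: r x (540 - C).

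Take C = 180 and 18 facility days seen (r = 10%). The literal score is 540 - 18 = 522, or 96.7% of 540, of which 360 days are unobserved. The observed record is 162 home days out of 180, or 90.0%; on a 540-day scale that is 486. The overstatement is 522 - 486 = 36 days. With no facility stay seen, the same person scores 540 of 540 on 180 observed days.

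For C from 90 to 360 and r from 5% to 20%, the overstatement runs from 0.05 x 180 = 9 to 0.20 x 450 = 90 days per affected participant.

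**3. The arm mean.** Overstatement = w x A x f, where w is the share losing access, A the true away-or-dead days per 540, and f the fraction of days unobserved. Uniform timing of the loss gives f = 270/540 = 0.5.

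| w | A | w x A x 0.5 |
|---|---|---|
| 2% | 30 | 0.3 days |
| 10% | 90 | 4.5 days |
| 10% | 180 (sicker withdrawers) | 9 days |

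The documents give none of w, A or f; all three are assumptions. The 10% is an upper case: it treats the whole planned dropout (SAP 6.1) as refusal of claims, whereas SAP 9.6 expects dropout below 10% and says that some dropouts will still permit claims use.

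**4. The contrast.** Only the difference between arms passes through.
- Equal w and equal A: no bias.
- Unequal loss, 10% against 2%, both with A = 90: 4.5 - 0.9 = 3.6 days of spurious difference.
- Equal w = 10% but A = 30 against 90: overstatements of 1.5 and 4.5, so a true difference of 60 shows as 57, an attenuation of 5%.

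**5. Does other text settle it?**
- Protocol 4.3.3 analyses all participants as randomized, and SAP 9.3 opens with intent to treat. No exclusion is stated for this outcome.
- The missing-at-random statement in SAP 9.6 covers the primary and secondary analyses, not tertiary ones.
- SAP 9.5 mentions censoring for the CMS day counts, but its answer is to treat them like time spent at home, which has no censoring rule.
- Protocol 8.4 says that its utilization models will allow for claims histories of different length, so unequal coverage is expected for related outcomes.

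**The case against.** A reader might infer that the plan scores every day after claims access ends as a home day, for everyone. The documents do not support that.
- No passage expressly keeps people who refuse claims use in this analysis. The bracket in protocol 6.1.3 can be read as limiting the outcome to people whose claims may be used. Crediting the days is the literal result of the formula, not a stated instruction.
- At the withdrawal level that keeps interviews, deaths are still reported at 3, 6, 12 and 18 months, so dead days are subtracted. Hospitalizations are also self-reported. Only full withdrawal loses everything.
- People lost to follow-up without withdrawing remain covered by claims and the health record, and SAP 5.5 looks up vital status there when the 18-month interview is missing. That search does not reach people who refused record access.

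A reader might also infer that withdrawal differs between active and usual care. That is plausible, but the documents say nothing on it. Nor do upper figures near 7 and 13 days follow from uniform withdrawal: they need f = 0.75 (10% x 90 x 0.75 = 6.75; 10% x 180 x 0.75 = 13.5).

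Three further objections stand in part. A fixed 540-day horizon is a legitimate target; what is missing is a rule for unobserved days. An offset for covered days assumes a constant rate, although dead days accumulate late, and it mixes horizons when deaths are counted to day 540 and others stop earlier. Finally, SAP 9.5 calls its model an initial approach and promises a fuller plan at tertiary data lock. That makes the point easy to correct, but it does not remove the conflict in the present text.

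**Conclusion.** The point holds as a conflict plus a gap. Protocol 6.1.3 describes person-specific follow-up, while its own formula, protocol 8.2.3 and SAP 5.5 and 9.5 all start from 540, and nothing says how days after loss of claims and record access are handled. Taken literally, the formula counts them as home days and the complement counts them as zero away days, apart from days after a known death.

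On the assumptions in the working (2-10% losing access, uniform timing, even accrual), an arm mean is overstated by about 0.3-4.5 days with 30-90 away-or-dead days, and by about 9 with 180. Bias in the contrast requires loss of access or away rates to differ by arm. The outcome is tertiary and exploratory, without multiplicity control, and primary and secondary conclusions do not depend on it. It should be corrected before tertiary data lock.

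**What to change.** In the SAP amendment already planned for tertiary data lock:

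1. Reconcile the person-specific description in protocol 6.1.3 with the 540-day formula there, in protocol 8.2.3 and in SAP 5.5 and 9.5.
2. State that days after claims and record access ends are missing, not days at home.
3. Define each person's observable days: 540 if covered throughout or known to have died, otherwise days to loss of access. Use these as the denominator or offset for days dead or in a facility.
4. State the analysis set and exclude people with no coverage. Say whether claims from before a withdrawal may still be used, since protocol 6.1 requests claims only at month 59.
5. Add a sensitivity analysis that does not assume a constant rate, such as inverse-probability-of-censoring weighting or multiple imputation to 540 days.
6. Apply the same rule to the CMS day counts that refer back to this method, and report loss of access by arm.

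The cost is one coverage-end date per person, which allowing for unequal claims histories under protocol 8.4 already needs, and slightly more analysis work.
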